Mitigating Automation Bias in Physician-LLM Diagnostic Reasoning Using Behavioral Nudges

[name], [name], [name],
[name], [name]

Study Protocol and Statistical Analysis Plan

Document Date: December 26, 2025

1 Introduction

Automation bias presents substantial risks in clinical environments, particularly as artificial intelligence (AI) tools become more integrated into healthcare workflows. This cognitive phenomenon describes the tendency of individuals to favor suggestions from automated decision-making systems, even when those suggestions are incorrect. While Large Language Models (LLMs), such as ChatGPT-5.1, hold promise for reducing diagnostic errors by augmenting clinical reasoning, concerns arise about their potential to amplify cognitive biases. Of particular concern is the propensity of LLMs to *hallucinate*, generating plausible but false information, which, when combined with automation bias, can lead clinicians to accept erroneous recommendations without adequate scrutiny.

The emergence of automation bias in medical contexts reflects a complex interplay of environmental and psychological factors. Time constraints in high-volume clinical settings create pressure to accept AI-generated recommendations without adequate scrutiny. Financial incentives that prioritize efficiency over thoroughness may further discourage the critical evaluation necessary for sound clinical judgment. Cognitive fatigue during extended shifts diminishes physicians' capacity for sustained analytical thinking. These contextual pressures interact with psychological mechanisms including diffusion of responsibility, overconfidence in technological solutions, and cognitive offloading, collectively creating conditions where uncritical acceptance of AI-generated recommendations becomes more likely.

This randomized controlled trial evaluates the effectiveness of a behavioral nudge intervention designed to mitigate automation bias among medical doctors utilizing LLM-generated diagnostic recommendations. The primary objective is to determine whether this intervention improves diagnostic reasoning performance scores when physicians evaluate clinical vignettes that include deliberately flawed LLM recommendations. Secondary objectives include assessing whether physician experience level, gender, and prior LLM experience moderate the intervention's effectiveness.

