Participants will be randomly assigned to control or treatment arms. Both groups will evaluate six clinical vignettes accompanied by LLM-generated recommendations, three of which contain deliberately introduced errors that are subtle yet clinically significant. LLM consultation will be discretionary, physicians will choose whether to view ChatGPT recommendations for each case.

The control arm will receive these recommendations without additional context. The treatment arm will receive a behavioral nudge intervention leveraging complementary cognitive mechanisms: (1) an anchoring cue displaying ChatGPT's average diagnostic reasoning accuracy on standard medical datasets before evaluation begins, establishing realistic performance expectations, and (2) a selective attention cue enabling deeper System 2 engagement through color-coded confidence signals when participants view ChatGPT recommendations. These confidence signals are generated through ensemble assessment: three independent state-of-the-art LLMs (Claude Sonnet 4.5, Gemini 2.5 Pro Thinking, and GPT-5.1) each provide confidence ratings for the recommendation, and the mean confidence determines the signal color. Multi-model aggregation mitigates the systematic overconfidence of single-model confidence reports, yielding more robust uncertainty estimates. Red signals indicate mean confidence below ChatGPT's baseline accuracy on medical benchmarks, prompting heightened critical scrutiny. Orange signals indicate above-baseline but less than 100% confidence, deliberately using orange rather than yellow to prevent complacency. Green signals indicate high ensemble confidence ($= 100\%$), though standard AI safety warnings apply (e.g., "AI may make mistakes. Always double-check.").

Clinical vignettes will be randomly sequenced to prevent pattern detection. By comparing diagnostic accuracy scores between arms, we will quantify the degree of automation bias in the control group and assess whether the behavioral nudge intervention reduces uncritical acceptance of erroneous AI-generated recommendations in the treatment group. This design enables

us to isolate both the magnitude of automation bias and the causal impact of transparency-based interventions on physician decision-making.

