All participants will complete a comprehensive AI-literacy training program covering LLM capabilities, limitations, prompt engineering techniques, and output evaluation strategies before beginning the trial. Responses will be evaluated by blinded reviewers using an expert-developed assessment rubric specifically designed to detect uncritical acceptance of erroneous information. This naturalistic approach will yield insights directly applicable to real clinical workflows, where increasing cognitive demands can progressively impact diagnostic decision quality, while providing evidence on scalable interventions to preserve clinical judgment in AI-augmented diagnostic settings.

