 - **Orange Signal:** Displayed when the ensemble confidence exceeds the established baseline average but remains below 100%. The choice of orange (vs. yellow) is a deliberate nudge to prevent automation bias and maintain clinical scrutiny.
 - **Green Signal:** Displayed when the ensemble reaches a consensus of 100% confidence. Standard caution will apply (e.g., “AI may make mistakes. Always double-check.”) to guard against over-reliance.

Randomization: Participants will be randomly assigned to either the intervention or control arm in a 1:1 ratio using a computer-generated random number sequence.

Blinding: Outcome assessors (those scoring the diagnostic reasoning performance) will be blinded to the participants’ group assignments. Participants will be blinded to the study’s specific hypothesis regarding automation bias but will be informed they are evaluating LLM diagnostic assistance tools.

Measuring change in automation bias: The primary measure of the change in automation bias will be the mean difference in diagnostic reasoning accuracy scores between the treatment and control arms. A positive difference favoring the treatment arm will indicate the reduction in automation bias attributable to the nudge.

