2.2 Participants

2.2.1 Inclusion Criteria

- Full or Provisionally Registered Medical Practitioners with the Pakistan Medical and Dental Council (PMDC).
- Completed Bachelor of Medicine, Bachelor of Surgery (MBBS) Exam. The equivalent degree of MBBS in the US and Canada is the Doctor of Medicine (MD).
- Participants must have completed a structured training program on the use of ChatGPT-4o (or a comparable large language model), totaling at least 10 hours of instruction. The program must include hands-on practice related to the LLM's key aspects, specifically prompt engineering and content evaluation.

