4.6 Exploratory Analyses

- **Differential Impact of Confidence Signals:** We will compare diagnostic scores for vignettes receiving Red Signal (flawed) versus Orange Signal versus Green Signal by group.

- **Chronometric Analysis of System 2 Engagement:** Using timestamps, we will compare time spent on Red Signal versus Orange Signal vignettes within the Treatment group. Longer durations on Red Signal vignettes would indicate deeper System 2 processing.
- **Physician-Case Specialty Match:** Exploratory analysis will test whether automation bias is lower when a vignette matches the physician's specialty, independent of AI accuracy or signal type.

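### The specialty-match analysis sets recommendation accuracy aside and names no vignette-level measure of automation bias, so subject knowledge could be read as lower bias

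*Combined protocol and SAP*

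**What the plan says.** The third item of section 4.6 reads: "Exploratory analysis will test whether automation bias is lower when a vignette matches the" physician's specialty, "independent of AI accuracy or signal type". Nothing else describes this analysis: no dependent variable, model or comparison is given.

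Section 1 describes automation bias as the tendency to "favor suggestions from automated decision-making systems, even when those suggestions are incorrect". It says that scores will be used to measure it: "By comparing diagnostic accuracy scores between arms, we will quantify the degree of automation bias in the control group". Section 2.1 repeats this for the nudge: "The primary measure of the change in automation bias will be the mean difference in diagnostic reasoning accuracy scores" between the arms.

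The outcomes are the composite score (section 3.1) and its final-diagnosis item (section 3.2). Section 1 also refers to a "rubric specifically designed to detect uncritical acceptance of erroneous information", but none of the five components listed in section 3.1 records whether the participant adopted the planted error. Whether the recommendation was opened is recorded for each vignette (section 2.5.1), but only a descriptive summary is planned (section 4.1). Three vignettes carry a flawed recommendation and three an accurate one. Both arms can view the recommendations, so there is no unaided comparison group.

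**The concern.** On the plan's own description, automation bias shows itself when the recommendation is wrong. An analysis of that bias that sets recommendation accuracy aside is at odds with the description. On the three accurate vignettes there is no error to accept, so a higher score there cannot show resistance to one.

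A physician working in their own specialty can be expected to score better whatever they do with the LLM. If correctness scores are the measure, that ordinary advantage goes straight into the match effect. What is at stake is one exploratory conclusion, that physicians are less prone to automation bias within their specialty, which could rest entirely on expertise.

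A smaller uncertainty concerns who counts as matched. Eligibility covers "Full or Provisionally Registered Medical Practitioners with the Pakistan Medical and Dental Council (PMDC"), and no rule says how a participant without a specialty would be handled.

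**Working it through.** **The plan's own figure.** The documents give no figure for this analysis. The one power statement (section 2.3, at least 80% with 50 participants) concerns the primary comparison. It reproduces: with 25 × 4/(1 + 3 × ICC) effective observations per arm, a difference of 8 and an SD of 16.2, power is 90.3% at ICC 0.05 (87.0 per arm) and 82.6% at ICC 0.15 (69.0 per arm). It has no bearing on this point.

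**What each contrast estimates.** Let B be the unmatched mean on accurate vignettes, K the knowledge gain on matched vignettes of either type, and L_u and L_m the points lost to a wrong recommendation when unmatched and matched.

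| | Accurate | Flawed |
|---|---|---|
| Unmatched | B | B − L_u |
| Matched | B + K | B + K − L_m |

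- Match effect, pooled or adjusted for accuracy as a main effect, with equal numbers of each type: K + (L_u − L_m)/2.
- Difference in the accurate-minus-flawed gap, unmatched minus matched: L_u − L_m.

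The first contains K in full; the second does not contain it.

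**Size of the knowledge term.** The final-diagnosis item carries 18 points. Section 3.1 does not say how many next steps are scored; assume three. Supporting and opposing findings are headed as up to 1 point per diagnosis, but their listed levels run to 2. Over three diagnoses the maximum is 3 + 3 + 3 + 18 + 3 = 30, or 3 + 6 + 6 + 18 + 3 = 36. The knowledge advantage is not in the documents, so a range is shown. Partial credit (9 points) is ignored.

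| Assumed advantage in correct final diagnosis | Points gained (× 18) | Score points, maximum 30 | Score points, maximum 36 |
|---|---|---|---|
| 5 percentage points | 0.9 | 3.0 | 2.5 |
| 10 percentage points | 1.8 | 6.0 | 5.0 |
| 15 percentage points | 2.7 | 9.0 | 7.5 |

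The last row is about the size of the 8-point effect planned for the trial. With the same advantage on both vignette types and equal L, the gap contrast is 9.0 − 9.0 = 0.

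**How often it would be significant.** The simulation used 50 participants and six vignettes (three flawed), SD 16.2 and ICC 0.10, with participant and vignette differences removed, so the main effect of accuracy is absorbed. Assumed: a loss of 15 points on flawed vignettes whether matched or not, so no true difference in bias, and every participant matching one or two vignettes. There were 2,000 runs per setting.

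| K (score points) | Match effect significant, 1 match | Match effect significant, 2 matches | Match-by-flawed interaction significant |
|---|---|---|---|
| 0 | 6% | 5% | 4–6% |
| 5 | 55% | 76% | 4–6% |
| 8 | 92% | 98% | 4–6% |
| 10 | 98% | 99.9% | 4–6% |

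The assumption that everyone has a match matters. With one match each among only some participants, the match effect is significant in roughly these shares of runs (simulation error of a few points):

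| Participants with a match | K = 9 | K = 5 |
|---|---|---|
| 10 | 39% | 15% |
| 20 | 63% | 28% |
| 50 | 95% | 56% |

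**Price of the interaction.** If the loss truly falls from 15 to 7 points on matched vignettes, with every participant having a match, the interaction is significant in about 32% of runs (one match each) to 46% (two).

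**The case against.** The strongest reply is that the plan never states the faulty rule. Section 4.6 leaves the analysis open, and nothing says that a higher score on matched vignettes will be taken as lower automation bias. That stands. A reader might infer that the plan equates the two, or that such a finding will be reported; the documents support only that the wording permits it.

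A reader might also infer that a positive result is nearly certain. That is not supported either. The probability runs from 15% to above 99% over the assumptions shown, and the number of matching pairs is not given.

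Section 2.1 also offers another reading: compare the arms within matched and within unmatched vignettes. An additive knowledge advantage then cancels. But this asks whether the nudge works differently with match, whereas section 4.6 asks whether bias is lower with match. The viewing indicator is a collected measure of reliance, but it is planned only for description and does not show that a wrong recommendation was accepted.

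It is likewise tempting to say that provisionally registered doctors will be coded as unmatched, adding inexperience to that group. The documents do not say so, nor that these doctors lack a specialty; there is simply no rule.

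Finally, the interaction is not fully clean. If knowledge adds K_f on flawed and K_a on accurate vignettes, the gap contrast becomes (L_u − L_m) + (K_f − K_a). A ceiling on accurate vignettes would make K_a the smaller and mimic lower bias. This stands as a limit on the remedy.

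**Conclusion.** The point holds as a defect in how the analysis is specified. With correctness scores as the only stated basis for automation bias, a match comparison that sets recommendation accuracy aside cannot distinguish expertise from resistance to a wrong recommendation. Neither pooling nor main-effect adjustment cures this, and the between-arm reading answers a different question.

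The direction of the problem follows from the algebra and needs only that physicians know more in their own field. The size rests on assumptions: 7.5 to 9 score points requires a 15-percentage-point advantage on both vignette types and three scored next steps, and smaller advantages scale down in proportion. The importance is low: this is one of three exploratory analyses and does not touch the primary or secondary outcome or the sample size.

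**What to change.** In section 4.6, replace the phrase "independent of AI accuracy or signal type" with a defined contrast, for example: *the match-by-recommendation-accuracy (flawed versus accurate) interaction on the diagnostic reasoning score will be estimated among participants who report a specialty; a smaller accurate-minus-flawed gap in matched than in unmatched physician-vignette pairs will be taken as indicating lower automation bias; the result is hypothesis-generating.* Restricting the analysis to participants who report a specialty also settles how those without one are handled.

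The cost is one sentence and one interaction term. Specialty is already collected, and recommendation accuracy is fixed by design. The price is precision: the 32 to 46% power above assumes that every participant has a match, so it would be lower with fewer. The report should therefore give the estimate with its confidence interval, not treat a non-significant result as evidence of no difference, and show scores on accurate vignettes by match so that a ceiling can be seen.

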4.7 Missing Data

- The primary analysis will be based on complete cases only.
- The pattern and extent of any missing data will be described.
- If substantial missing data occurs ($\geq 5\%$ for any key variable), multiple imputation will be considered, and results will be compared to complete case analysis.

4.8 Statistical Software

All statistical analyses will be performed using R (version 4.3.2 or later) with appropriate packages (e.g., 'lme4', 'ordinal', 'mice') or equivalent softwares in Python or Stata.

5 Risks, Harms & Ethical Considerations

5.1 Potential Risks and Harms

This study poses minimal risk to participants. Some participants may experience mild discomfort or frustration, particularly those in the control group who may find clinical case studies challenging without LLM assistance.

5.2 Safeguards for Addressing Risks or Harms to Subjects

To minimize potential discomfort, participants will receive comprehensive instructions and ongoing support throughout the study. Participants will be informed that individual performance is not being evaluated, and that data will be analyzed for aggregate trends only. All participants will be advised of their right to withdraw from the study at any time without penalty or explanation. Research staff will monitor for signs of distress and provide appropriate support as needed.

5.3 Informed Consent

Informed consent will be obtained from all participants before enrollment in the study.

5.4 Participant Compensation

Participants will receive a complimentary one-month subscription to ChatGPT Plus (or equivalent) after completing the study. Additionally, each participant will receive a certificate of participation to formally acknowledge their valuable time and effort in contributing to this research.

